## AMENDMENT HISTORY

SAP Version	Issue Date
Original SAP	15 March 2018
Amendment 1	25 February 2020
Amendment 2	13 January 2022

### Amendment 2 (13 January 2022)

**The overall reason for the amendment:** to update and clarify the details.

Applicable Section(s)	Description of Change (s)
Section 4.4	Added 'COVID-19 related protocol deviations will be provided in a separate listing'.
Section 6.1.1	Updated the definition of Cardiac arrhythmia as 'Cardiac arrhythmia will be determined based on Cardiac arrhythmias (SMQ, broad and narrow) and Ventricular tachyarrhythmias (SMQ, narrow)'.
Section 6.1.1	Updated the definition of CNS hemorrhage to remove manual medical review.
Section 6.1.1	Added ischemic stroke and cardiac failure for AE of special interest.

### Amendment 1 (25 February 2020)

**The overall reason for the amendment:** to update and clarify the details.

Applicable Section(s)	Description of Change (s)
Section 2.9	Added 'Assigned daily dose is 420 mg, unless dose is modified due to the use of CYP3A inhibitor or study drug discontinuation'.
Section 4.1	Added 'Daily Steroid Dose per Weight at baseline (mg/kg/day)' to baseline disease characteristics information.
Section 4.3	Added 'Time on study'.
Section 4.5	Added 'Medical history collected at baseline or screening visit will be summarized by system-organ class and preferred term for all treated analysis set'.
Section 4.6	Change from 'the day of ICF (partial or complete) of study agent' to 'the first dose of the study agent'. Added 'Concomitant use of additional immunosuppressants will be summarized and listed'.
Section 6.1	Updated planned tables.
Section 6.1.1	Added AEs of special interest, 'Other Malignancies', 'Hypersensitivity' and 'CNS Hemorrhage'.
Section 6.2	Added subjects who died during the study.
Section 6.5	Added subjects who died in the study.
Section 7.1	Added Subgroup analysis by concomitant CYP3A inhibitors.

## ABBREVIATIONS

AE	adverse event
ALT/SGPT	alanine aminotransferase
AST/SGOT	aspartate aminotransferase
BTK	Bruton's Tyrosine Kinase
BUN	blood urea nitrogen
cGVHD	Chronic Graft Versus Host Disease
CI	confidence interval
Cmax	maximum concentration
CR	complete response
CRF	case report form
CTCAE	Common Terminology Criteria for Adverse Events
CV	coefficient of variation
DOOR	duration of response
ECG	electrocardiogram
eCRF	electronic case report form
FAS	full analysis set
FEV1	forced expiratory volume in 1 second
FFS	failure free survival
LDH	lactic acid dehydrogenase
ILD	interstitial lung disease
MedDRA	Medical Dictionary for Regulatory Activities
OS	Overall survival
PD	pharmacodynamic
PI	principal investigator
PK	pharmacokinetic(s)
PR	partial response
PT	preferred term
SAE	serious adverse event
SAP	Statistical Analysis Plan
SD	standard deviation
SOC	system organ class
SMQs	standardised MedDRA queries
TEAE	treatment-emergent adverse event
Tmax	time to maximum concentration
WBC	white blood cell
WHO	World Health Organization
WHO-DD	World Health Organization Drug Dictionary

## 1. INTRODUCTION

This Statistical Analysis Plan (SAP) covers Primary Analysis and Final Analysis. It contains definitions of analysis sets, derived variables and statistical methods for analyses of efficacy, safety, pharmacokinetic (PK) and pharmacodynamics (PD) data of study 54179060GVH3001.

### 1.1. Trial Objectives

#### **Primary objective:**

Evaluate efficacy of ibrutinib in Japanese subjects with steroid dependent/refractory cGVHD by measuring overall cGVHD response (Complete Response [CR] and partial response [PR] defined by NIH Consensus Development Project Criteria [2014]).

#### **Secondary objectives:**

- Evaluate efficacy of ibrutinib in Japanese subjects with steroid dependent/refractory cGVHD by measuring:
  - Rate of sustained response for at least 20 weeks
  - Duration of response (DOR)
  - cGVHD response rate at each timepoint of efficacy evaluation
  - Corticosteroid requirement changes over time
  - Change in symptom burden measured by the Lee cGVHD Symptom Scale
- Evaluate the safety of ibrutinib in Japanese subjects with steroid dependent/refractory cGVHD
- Evaluate the pharmacokinetics (PK) of ibrutinib in Japanese subjects with cGVHD

#### **Exploratory objectives:**

- Evaluate efficacy of ibrutinib by measuring:
  - Failure free survival (FFS)
  - Overall survival (OS)
  - Number and proportion of subjects with all immunosuppressants withdrawn
- Evaluate the BTK and ITK binding site occupancy as a pharmacodynamic (PD) parameters

### 1.2. Trial Design

This is an open-label, single arm, multicenter Phase 3 study to evaluate the efficacy, safety, and PK of single-agent ibrutinib 420 mg in Japanese subjects 12 years of age or older with steroid dependent/refractory cGVHD. Approximately 20 subjects will be enrolled to have 17 response evaluable subjects. At least 1 adolescent subject (12-17 years of age) will be enrolled in this study.

Subject participation will include a Screening Phase, a Treatment Phase, and a Posttreatment Follow-up Phase. The Screening Phase assessments will be performed within 42 days prior to study treatment initiation. The Treatment Phase will extend from first dose of study treatment until treatment discontinuation. During the Treatment Phase, efficacy and safety evaluations, sampling of PK and PD will be performed. The Posttreatment Follow-up Phase will begin once a subject discontinues ibrutinib treatment. Subjects who discontinue treatment for reasons other than cGVHD progression will complete an End-of-treatment Visit and will be followed for the cGVHD evaluations until cGVHD progression, death, loss to follow-up, consent withdrawal, or study end, whichever occurs first. Subjects who discontinue due to cGVHD progression will complete an End-of-treatment Visit and be followed for survival status and the use of subsequent cGVHD treatment.

### **1.3. Statistical Hypotheses for Trial Objectives**

The primary hypothesis of this study is that ibrutinib is an effective agent as measured by an overall cGVHD response rate (the lower bound of 95% confidence interval is greater than 25%) in Japanese subjects with steroid dependent/refractory cGVHD.

### **1.4. Sample Size Justification**

With a sample size of 17 subjects and assuming an expected overall cGVHD response rate of approximately 60%, it is expected to have at least 80% power to show the efficacious treatment effect (the lower bound of 95% confidence interval of the response rate >25%). At least 1 adolescent subject (12-17 years of age) will be enrolled in this study.

### **1.5. Randomization and Blinding**

This is an open label study, so no randomization and blinding will occur.

## **2. GENERAL ANALYSIS DEFINITIONS**

### **2.1. Visit Windows**

For visitwise analysis, CRF-recorded visits will be followed.

The visit windows are described in “Time and Events Schedule” of the protocol. For visitwise evaluation of pharmacokinetics and pharmacodynamics data of ibrutinib, allowance described in “Time and Events Schedule” will be applied to actual time of CRF-recorded time point.

### **2.2. Pooling Algorithm for Analysis Centers**

No pooling of analysis centers will be performed in this study.

### **2.3. Analysis Sets**

#### **2.3.1. All Treated Analysis Set**

The all treated analysis set includes all enrolled subjects who received at least 1 dose of study drug.

### **2.3.2. Response Evaluable Analysis Set**

All enrolled subjects who will receive at least 1 dose of study drug and who have at least 1 adequate postbaseline efficacy assessment.

### **2.3.3. Safety Analysis Set**

The safety analysis set includes all enrolled subjects who received at least 1 dose of study drug. Safety analysis set is identical to all treated analysis set.

### **2.3.4. Pharmacokinetics Evaluable Analysis Set**

The PK evaluable analysis set is defined as all enrolled subjects who have received at least one dose of study drug and have at least 1 postdose PK sample obtained.

### **2.3.5. Pharmacodynamics Evaluable Analysis Set**

The PD evaluable analysis set is defined as all enrolled subjects who have received at least one dose of study drug and have at least 1 BTK and ITK binding site occupancy data.

## **2.4. Study Day and Relative Day**

Study Day 1 or Day 1 refers to the start of the first study drug administration. All efficacy and safety assessments at all visits will be assigned a day relative to this date.

Study day or relative day for a visit is defined as:

- Visit date - (date of Study Day 1) +1, if visit date is  $\geq$  date of Study Day 1
- Visit date - Date of Day 1, if visit date  $<$  date of Study Day 1

There is no 'Day 0'.

## **2.5. Baseline**

Baseline is defined as the last observation on or prior to the first study drug administration.

## **2.6. Treatment Duration**

Treatment duration will be calculated from the date of the first dose of study drug to the date of the last dose of study drug, as follows:

Treatment Duration = date of last dose of study drug – date of first dose of study drug +1 day.

## **2.7. Time on Study**

Time on Study will be calculated from the first study drug administration date to the study exit date or the last known alive date if the subjects are still in the study, as follows:

Time on Study = study exit date/last known alive date – first study drug administration date +1 day.

## 2.8. Dose Intensity

The dose intensity (mg/day) of study agent is calculated as (sum of total daily dose during the treatment phase)/study agent duration.

## 2.9. Relative Dose Intensity

Relative dose intensity (%) is defined as the percentage of total cumulative dose administered (mg) versus the total expected dose (mg). Total cumulative dose administered is the sum of daily dose taken over the whole study course; and total expected dose (mg) is the product of the duration of the treatment (day) and the assigned daily dose. Assigned daily dose is 420 mg, unless dose is modified due to the use of CYP3A inhibitor or study drug discontinuation. Relative dose intensity is calculated by total cumulative dose administered / total expected dose  $\times 100\%$ .

## 2.10. Imputation Rules for Missing Dates

In general, imputation of missing dates will be made for AE onset date, AE resolution date, date of death, start and end dates of prior and concomitant and subsequent therapies, transplantation date, and date of initial diagnosis according to the following rules.

- If the date is completely missing, no imputation will be made.
- If the year is missing, then no imputation will be made.
- If only the year is present but the month and day are missing, then June 30th will be used.
- If only the day is missing but the year and month are available, then the 15th of the month will be used.

In addition, for date of initial diagnosis, the imputed date will be adjusted sequentially using the following steps:

- If only the day is missing;
  - if month and year of start of 1st line of prior therapy are the same year and month of diagnosis, and day of start date of 1st line of prior therapy is available, then the day of start date of 1st line of prior therapy will be used.
  - otherwise, the 15th of the month will be used.
- If both month and day are missing;
  - if year of diagnosis is the same as year of start of 1st line of prior therapy, and month info is available for start date of the 1st line of prior therapy, the month of start date of 1st line of prior therapy will be used.
    - if day of start date of 1st line of prior therapy is available, then the day of start date of 1st line of prior therapy will be used.
    - otherwise, the 15th of the month will be used.
  - otherwise, June 30th will be used.

- If the imputed date for initial diagnosis is on or after the first dose date, then first dose date -1 day will be used.

In addition, for date of prior and subsequent therapies, the imputed date will be adjusted sequentially using the following steps:

- If such imputed date for prior therapies is on or after the first dose date, then first dose date -1 day will be used.
- If such imputed date for subsequent therapies is before date of last dose, then date of last dose +1 day will be used.
- If prior or subsequent therapy start date is not missing and is after the imputed end date, then the start date will be used as the end date.
- If prior or subsequent therapy end date is not missing and is before the imputed start date, then the end date will be used as the start date.

In addition, for AE date, the above imputations will be modified by the following rules:

- The imputed start date of adverse event will be adjusted sequentially using the following steps:
  - If the imputed date is in the same year and month but before the first dose date, then the first dose date will be used, or if it is in the same year and month but after the last dose date +30 days, then the last dose date +30 days will be used.
  - If end date of adverse event is not missing and the imputed start date of adverse event is after the end date of adverse event, then the end date of adverse event will be used.
  - If the imputed start date of adverse event is after date of death, then the date of death will be used.
  - If the imputed start date of adverse event is in the same month and year but after the start date of 1st subsequent therapy, then the start date of 1st subsequent therapy will be used.
- The imputed end date of adverse event will be adjusted sequentially using the following steps:
  - If the imputed end date of adverse event is after the death date, then the death date will be used.
  - If the imputed end date of adverse event is before the start date of adverse event, then the start date of adverse event will be used.

In addition, for start and end dates of concomitant therapy, the adverse event imputation rule will be used for concomitant therapy.

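### SAP 2.10 imputes partial death dates to the 15th or June 30 with no consistency bound, so a death can be dated before last documented contact and, in narrower cases, before first dose

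*SAP*

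**What the plan says.** SAP 2.10 opens with the dates it covers: "AE onset date, AE resolution date, date of death, start and end dates of prior and concomitant and subsequent therapies", followed by transplantation and initial diagnosis. Two general rules apply to all of them. One is "If only the year is present but the month and day are missing, then June 30" of that year. The other begins "If only the day is missing but the year and month are available" and uses the 15th of the recorded month. A date with no year is not imputed.

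The section then adds consistency steps by type of date:

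- **Initial diagnosis:** "If the imputed date for initial diagnosis is on or after the first dose date, then first dose date -1 day will be used".
- **Subsequent therapy:** "If such imputed date for subsequent therapies is before date of last dose, then date of last dose +1 day will be used". Prior therapy is likewise kept before first dose.
- **AE start:** "If the imputed date is in the same year and month but before the first dose date, then the first dose date will be used". The AE rules also serve for concomitant therapy.

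No step adjusts an imputed date of death. The death date enters only as a limit on other dates, for example "If the imputed end date of adverse event is after the death date, then the death date will be used"; imputed AE start dates have a matching limit.

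No other section fills the gap. SAP 5.1.2 sends partial dates back to 2.10. The definitions of DOR (5.3.1, Table 2), FFS (5.4.1, Table 4) and OS (5.4.1) use the date of death without a rule for partial ones. The last known alive date appears in SAP 2.7, for time on study, and only for subjects still in the study.

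**The concern.** Date of death is an event date in three time-to-event endpoints: DOR (secondary), FFS and OS (exploratory). A mid-month or mid-year default is harmless only while it does not contradict what is already known. Here nothing stops it from doing so. A programmer following the text could produce a death before a visit the subject attended, or a negative survival time. Someone would then have to choose a correction after seeing the data.

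The gap looks like an omission. The SAP bounds the comparable dates, and its note to Table 2 requires an imputed start of subsequent cGVHD treatment to be compatible with the last dose date.

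**Working it through.** The plan gives no figure for this rule, so there is none to reproduce. The check applies SAP 2.10 literally.

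**Rule**

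- Day missing: imputed death = 15th of the recorded month.
- Month and day missing: imputed death = June 30 of the recorded year.

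**Largest early error**

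- Day missing, true death on the 31st: 31 − 15 = 16 days.
- Year only, true death on December 31: 31 + 31 + 30 + 31 + 30 + 31 = 184 days (July to December).

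**When the result contradicts known dates**

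- Before last contact: the last contact falls after the 15th of the month of death (day missing), or after June 30 of the year of death (year only).
- Before first dose: the first dose was given after the 15th and death is in the same month (day missing), or after June 30 and death is in the same year (year only).

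**Illustrations.** All dates are assumed, in 2019. OS = death − first dose, in days. The floor is the later of the imputed date and the last visit.

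| Case | First dose | Last visit | True death | Known part | Imputed | Days before last visit | OS imputed | OS with floor | OS true |
|---|---|---|---|---|---|---|---|---|---|
| A | 7 Jan | 23 Sep | 28 Sep | month, year | 15 Sep | 8 | 251 | 259 | 264 |
| B | 7 Jan | 23 Sep | 10 Nov | year | 30 Jun | 85 | 174 | 259 | 307 |
| C | 18 Mar | 25 Mar | 29 Mar | month, year | 15 Mar | 10 | −3 | 7 | 11 |
| D | 5 Aug | 28 Oct | 20 Nov | year | 30 Jun | 120 | −36 | 84 | 107 |

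**How often a partial death date would conflict.** Let the true death fall on each day of 2019 in turn, with last contact g days earlier. Share = (days on which the imputed date is before last contact) / 365.

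| Gap g (days, assumed) | Day missing | Year only |
|---|---|---|
| 1 | 47.4% | 50.1% |
| 7 | 27.7% | 48.5% |
| 14 | 4.9% | 46.6% |
| 28 | 0.0% | 42.7% |
| 84 | 0.0% | 27.4% |

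For example, with year only and g = 84, the conflict needs a death after September 22: 8 + 31 + 30 + 31 = 100 days, and 100/365 = 27.4%. The 84 days match the 12-weekly survival follow-up after progression (Protocol 9.1.1).

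**Effect by endpoint**

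- **OS:** the death stays an event; its time is wrong.
- **FFS:** Table 4 counts death, new cGVHD treatment and relapse as events, and the earliest counts. A death imputed to June 30 ahead of a new treatment recorded in August replaces that event and its date.
- **DOR:** Table 2 takes progression or death, whichever is earlier. A death imputed to June 30 displaces a progression documented in August. Table 2 also counts a death on or before the start of new cGVHD treatment as an event. A response that should be censored at new treatment can therefore become an event. If the imputed death precedes first response, DOR is negative.
- **AEs:** an AE date that was itself imputed is cut back to the early death date.

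**The case against.** The best defence is that this will rarely matter, and most of it stands.

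- **Frequency.** The documents give no expected number of partial death dates. Survival is followed every 12 weeks after progression, data queries are provided for (Protocol 17.5), and serious adverse events are reported within 24 hours (Protocol 12.3.2), although deaths from cGVHD progression are exempt. Year-only dates should be unusual. With only the day missing, the conflict needs a death soon after the last contact.
- **Direction.** A mid-period default errs late as well as early. The 16 and 184 days are early maxima, not expected errors or evidence of general bias.
- **DOR and FFS.** Telephone follow-up, where partial dates are most plausible, is for subjects who have already progressed. Their DOR has normally ended by then, and FFS often ends at new treatment. These endpoints change only if the imputed death falls before those dates.
- **Consequences.** The primary endpoint is a binomial response rate, and DOR, FFS and OS are summarised descriptively.

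Three stronger readings are tempting but unsupported. A reader might infer that AE dates in general are cut at the wrong death date; SAP 2.10 cuts only imputed AE dates, so the carry-over needs a partial death date and a partial AE date in one subject. A reader might also say that one misdated death is worth 1/17 = 5.9 points of the curve. In OS the step remains and only moves in time, and DOR covers responders only, about 17 × 0.60 = 10 subjects at the planned rate. Finally, a reader might take the last known alive date as already available from SAP 2.7, but that section does not apply it to subjects who died.

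None of this supplies the missing bound.

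**Conclusion.** The rule is wrong as written, with low practical weight. It can place a death before documented contact and, under the two stated conditions, before first dose. The early error is at most 16 days with the day missing and 184 days with only the year known. OS, FFS and DOR times, some DOR event or censoring assignments, and imputed AE dates can be affected. The trial's success criterion cannot be.

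The conclusion rests on the text of SAP 2.10 alone. The illustrative dates and contact gaps are assumptions, and the shares are conditional on a death date being partial. That few subjects will be affected is a judgement, since the documents give no count.

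**What to change.** Add to SAP 2.10:

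> *If the imputed date of death is earlier than the last date the subject is documented alive (last visit, assessment, dose or survival contact), that last documented alive date will be used as the date of death.*

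State also, there or in SAP 2.7, that this date is derived for subjects who died as well as for those still in the study.

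Do not add one day to the floor. A subject seen on September 30 whose death is recorded as September would then be dated October 1, outside the recorded month. Without the extra day the floor cannot leave the recorded period, because the last documented alive date cannot be later than the true death.

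The floor removes the contradiction in all four cases above. It does not recover the true date: in case B, OS becomes 259 days against a true 307. The cost is one or two sentences and one derived date from data already collected, with no change to conduct or sample size.

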### **3. INTERIM ANALYSIS AND DATA MONITORING COMMITTEE REVIEW**

No interim analysis will be conducted in this study.

## 4. SUBJECT INFORMATION

### 4.1. Demographics and Baseline Characteristics

List of the demographic and baseline characteristics, presented in [Table 1](#), will be summarized for the all treated analysis set.

**Table 1: Demographic and Baseline Characteristics Variables**

Continuous Variables:	Summary Type
Age (years)	Descriptive statistics (N, mean, standard deviation [SD], median and range [minimum and maximum].)
Weight (kg)	
Height (cm)	
Baseline hemoglobin (g/L)	
Baseline platelets ( $10^9/L$ )	
Baseline Absolute neutrophil count ( $10^9/L$ )	
Baseline Bilirubin	
Categorical Variables	
Sex (male, female, unknown,undifferentiated)	Frequency distribution with the number and percentage of subjects in each category.
Race (Asian)	
Ethnicity (Hispanic or Latino, not Hispanic or Latino)	

Following baseline disease characteristics information will be summarized for all treated subjects:

- cGVHD Disease State (Steroid Dependent, Steroid Refractory)
- Overall Severity of cGVHD (1, 2, 3, NA)
- Months from Last Transplantation to Enrollment, which is defined as the time period between the last transplantation and enrollment
- Months from Initial cGVHD Diagnosis Date, which is defined as the time period between the initial cGVHD diagnosis and enrollment
- Months from Transplantation to initial cGVHD diagnosis date
- Karnofsky performance status score at baseline
- Lansky performance status score at baseline
- Number of prior cGVHD treatment regimens
- Organs involved in cGVHD
- Daily Steroid Dose per Weight at baseline (mg/kg/day)

